4.6.2 Follow-up for Withdrawn Subjects

If a subject withdraws from the study, any recorded data will still be included in the analysis. Subjects will only be replaced if they withdrew prior to undergoing GAE.

5.0 Study Treatment or Diagnostic Product Procedures

5.1 Description

Subjects will not initiate any new pain therapy or escalate current therapy for 1 month prior to GAE. They will be given an intravenous dose of antibiotics on the day of the procedure and continue with oral antibiotics for seven days after the procedure. The subjects will be given the choice of receiving intravenous anxiolytic and analgesic medication during procedure or proceeding with local anesthetic only.

Arterial access site will be prepped and draped using sterile technique. Ultrasound-guided access may be used and arterial access will be obtained. An intra-arterial sheath will be placed. Through this sheath a guiding catheter will be used to perform lower extremity angiography on the targeted side either manually or robotically. Using the guiding catheter and a microcatheter, the geniculate arteries supplying hypervascular synovial tissue in the region of the knee joint will be catheterized. If there is uncertainty about the angiographic findings, pre-embolization simulation can be performed with contrasted cone beam CT on the procedure table. This will allow

the operators to know exactly what tissues will be receiving the microspheres. Embosphere Microspheres ranging from 40-500 microns*, selected at the operator's discretion based upon size of target vessels, will then be injected under fluoroscopic guidance to prevent reflux and non-target embolization. Injection will continue until an end point of at least 'near stasis' (slowed antegrade flow of contrast). Multiple geniculate arteries may be embolized until neovascularity is no longer seen. A repeat lower extremity angiogram will then be performed to evaluate for success of embolization and to exclude complication. The catheter and sheath will then be removed and hemostasis will be achieved with manual compression or a vascular closure device. The subject subsequently will be discharged home the same day (<23 hours) unless a complication arises that requires inpatient admission for management of the complication. Subjects may be discharged on pain medications as needed for post-operative care (<14 days).

**The range in size of particles will allow the operators to discern the safest, most effective size for the vessels targeted. For example, if the catheter can be advanced all the way in to the branch supplying only the synovium, smaller particles can be safely used to induce ischemia in the target tissue. If the catheter cannot be advanced due to tortuous or small caliber vessels, a larger sized particle may be selected. This will allow for proximal embolization without distal penetration into the cutaneous branches, thereby allowing continued blood flow to the skin through collateral pathways (Fig 1-2). This concept is utilized routinely within embolization procedures are commonly performed.*

[figure not shown]

Fig 1.-Geniculate artery angiogram after total knee arthroplasty demonstrating “contrast blush” denoting hypervascular synovium (bold arrow). Separate arterial branches are seen supplying the joint tissue (arrow) and skin (dotted arrow). At this point an attempt would be made to place a microcatheter in the synovial branch. If impossible due to the size of the target vessel, embolization would be performed from this catheter location using larger particles to preserve distal collateral supply to the skin.

[figure not shown]

Fig 2. Lateral angiogram of the knee with selective catheterization of the synovial branch of the geniculate artery. In this circumstance, smaller sized embolic particles would be appropriate because cutaneous branches are not seen. This could also be verified with cone beam CT prior to embolization.

It is anticipated that less than 20 milliliters of Embozene will be required for embolization. Embozene Microspheres currently have FDA approval for embolization of hypervascular tumors and arteriovenous malformations.

5.2 Method for Assigning Subject to Treatment Groups

Because this is a pilot study to assess feasibility, all subjects will receive the study intervention (GAE).

5.3 Subject Compliance Monitoring

Study coordinators and physicians will inquire of the subjects to confirm that they have not initiated any new conservative therapies during the follow-up period.

5.4 Prior and Concomitant Therapy

The subjects will be required to have been on conservative therapy for OA for at least three months prior to undergoing GAE. They will be allowed to continue previously initiated therapies throughout the study period, but no new or escalated therapies will be permitted, except post-operative medications (<14 days).

5.5 Blinding of Study

As a pilot study to assess feasibility, all subjects will receive GAE. Therefore, neither the study physicians nor subjects will be blinded to the treatment protocol.

5.6 Receiving, Storage, Dispensing and Return

5.6.1 Receipt of Investigational Device Supplies

Embozene Microspheres will be stored within the Interventional Radiology procedural suites. Embolic devices will be labeled 'for investigational use only' and will be reserved for use in the clinical trial.

5.6.2 Storage

Embozene Microspheres must be stored in a cool, dark, dry place in their original packing.

5.6.3 Dispensing

No study specific dispensing techniques will be used.

5.6.4 Return or Destruction of Investigational Device

Embozene Microspheres can be used for other FDA approved indications and will not be destroyed or returned at the completion of the study. Disposable syringes which spherical particulate is stored in will be discarded as medical waste and packaging will be kept in a secure location until the study is completed. Packages will be disposed of upon completion of the study.

6.0 Study Procedures

6.1 Visit 1

Potential enrollees will first be identified and will undergo a standard knee OA work-up to include history and physical exam with emphasis on specific site of knee tenderness. The Western Ontario and McMaster University Osteoarthritis Index (WOMAC) questionnaire will be administered to assess difficulty as a result of pain, stiffness and overall decreased function secondary to knee pain in the past week. Current pain will also be assessed using a visual analog scale (VAS). A knee radiograph will be obtained and evaluated using the Kellgren-Lawrence grading scale. A baseline knee MRI will also be acquired to evaluate for concomitant pathology as part of routine orthopedic evaluation. For patients that have had an MRI of the knee within the past 90 days, the previous knee MRI will be used as the baseline MRI and new imaging will not be obtained.

If a patient qualifies to be a subject in the study based on the inclusion and exclusion criteria listed in section 4.3 and 4.4, the local study coordinator, co-principal investigator or designee will provide the candidate with a copy of the approved

informed consent and introduction letter for the candidates' review. Written informed consent will be obtained if appropriate. If the patient wishes to take more time to review the study before enrolling, he/she may complete the consent process at the beginning of the next visit, prior to the study GAE procedure. Those candidates who are disqualified from study entry will be logged into the Screening Log with a reason for no study entry. A copy of the consent will be provided to the subject and the original filed in the study files.

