4.3 Inclusion Criteria

1. Moderate to severe knee pain (VAS > 50 mm), and
2. Pain refractory to at least 3 months* of conservative therapies (anti-inflammatory drugs, or physical therapy, or muscle strengthening, or intra-articular injections), and
3. Kellgren-Lawrence grade 1, 2 or 3 on radiograph of the knee.
4. Age > 40 years.

*3 months was chosen because this time interval is thought adequate for knee pain to be considered refractory to conservative care.

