6.2 Visit 2 GAE

GAE will be performed as described in part 5.1 above within 4 weeks of Visit 1. Subjects will be given a pager number to reach a physician 24 hours a day to report any adverse symptoms and receive medical advice.

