6.7 Study Procedure Flow Chart

7.0 Safety and Effectiveness Assessments

7.1 Safety Assessments

Subjects will be observed for several hours after GAE to monitor for immediate complications to include bleeding, infection and acute ischemia of the lower extremity. The subjects will be given a phone number that they can call to reach the principal investigator or designee if they believe they have developed a complication of the procedure.

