9.0 Risk Analysis

9.1 Anticipated Risks

Previous studies of lower extremity geniculate artery embolization for arthritis related pain have reported only one complication of moderate puncture site related hematoma (1/13), however this was a small population (12). A recent study of GAE for recurrent hemarthrosis completed by one of the co-PIs ([name]) included 2/13 subjects who developed transient cutaneous ischemia that resolved within three weeks without intervention (8). Additional risks that are anticipated but occur infrequently after any arterial intervention include infection, pain, pseudoaneurysm formation, arterial dissection and distal non-target embolization resulting in ischemia or necrosis. Detailed risk analysis is below:

	Risk or Side Effect	Source of Risk or Side Effect	Possible	Less Possible	Rare Event
Potential Risks Associated Study Enrollment & Study Procedures	Discomfort	Blood draw for lab test, ultrasound or MRI	X		
	Thrombophlebitis, bruising, bleeding, blood clot, Pre-syncope or Syncope (i.e. Fainting)	Blood draw for lab tests		X	
	Anxiety or Claustrophobia	MRI scan		X	
	Psychological Discomfort	Clinical Trial Enrollment			X
	Infection	Blood draw for lab tests			X
	Allergic Reaction	MRI contrast injection			X
	Gadolinium contrast adverse reaction (ie. Nephrogenic Systemic Fibrosis or severe skin reaction from contrast agent only reported in patients with kidney dysfunction)	MRI Contrast injection			X
	Confidentiality breach from Medical Records	Medical Record Keeping			X
	Groin/Anesthetic Injection/Neurologic Injury/Discomfort/Pain	Pressure during arterial access and after catheter removed at the leg/femoral artery site	X		
	Radiation Exposure Injury	GAE procedure			X
	Kidney Dysfunction	Contrast injected during procedure		X	

Risks of the GAE Procedure and Postoperative care	Joint Infection	GAE Procedure		X	
	Adverse or Allergic Reaction	Intravenous contrast agent or medications administered as part of procedure or follow-up care (ie. MRI contrast)		X	
	Tissue damage to Skin, Muscle, Skin or other structure in legs (Non-target Embolization)	GAE procedure			X
	Minor Bruising or Bleeding	GAE procedure			X
	Bleeding requiring Transfusion or surgery	GAE procedure			X
	Synovitis related symptoms including pain, stiffness or limited joint mobility	GAE procedure	X		
	Post Embolization Syndrome, including fever, malaise, headache, and myalgia (body aches)	GAE procedure		X	

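### The plan does not say which VAS is baseline; if it is the Visit 1 reading used for entry, the single-arm VAS change is expected to include some regression to the mean

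*Combined protocol and SAP*

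**What the plan says.** Section 4.3 requires "Moderate to severe knee pain (VAS > 50 mm), and" and also "Pain refractory to at least 3 months* of conservative therapies". Section 6.1 (Visit 1) gives the pain measurement as "Current pain will also be assessed using a visual analog scale (VAS"; its next paragraph checks the candidate against sections 4.3 and 4.4. Consent may be deferred: "he/she may complete the consent process at the beginning of the next visit, prior to the study GAE procedure". Section 6.2 states "GAE will be performed as described in part 5.1 above within 4 weeks of Visit 1" and names no VAS or WOMAC; the procedure description in 5.1 names none either. Scheduled VAS and WOMAC readings resume at 1, 3 and 6 months after GAE (6.4 to 6.6).

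Section 7.2 defines the VAS criterion as a 15% fall from baseline at 6 months, and 8.2 applies a paired t-test from baseline to 6 months. Neither says which reading is baseline. Section 8.2 describes what the test measures as change caused by the procedure. All subjects receive GAE, unblinded (5.2, 5.5). The VAS criterion is a primary endpoint in 3.2 and a secondary outcome in 7.2 and 8.1.

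**The concern.** When subjects enter because a score was high on one occasion, part of that height is usually temporary. If the same reading is then the starting point for change, the later mean is expected to be lower even if nothing was done, for any test-retest correlation below 1. A single reading of current pain gives no averaging to reduce this. In a single-arm study this fall cannot be separated from a treatment effect, and the paired t-test counts it as change.

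At stake are the error rate of the VAS test, the VAS responder percentage, and any VAS change carried into planning a later study, which section 2.0 gives as an aim.

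**Working it through.** **The plan's own figure.** Section 8.1 gives no figure for the VAS. Its WOMAC figure reproduces: 7.8 points, SD 10 taken as the SD of the change, n = 15, two-sided 0.05. The noncentrality is 7.8/(10/√15) = 3.02 on 14 df, and power is 0.802 against the stated 80%. This does not bear on the VAS.

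**Inputs for the VAS.** From the documents: threshold 50 mm (4.3), alpha 0.05 (8.2), n = 15 and 20 (8.1). Assumed, because the documents give none: mean μ and SD σ of the VAS in screened patients, correlation r between Visit 1 and 6 months, normality, and a two-sided test.

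**Formula.** With a = (50 − μ)/σ and λ = φ(a)/(1 − Φ(a)), the mean of those selected is μ + σλ. The expected fall at retest with no treatment effect is (1 − r)σλ.

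**One assumed case: μ = 60, σ = 20, r = 0.7.**
- a = −0.5 and λ = 0.3521/0.6915 = 0.509.
- Selected mean: 60 + 20 × 0.509 = 70.2 mm.
- Fall: 0.3 × 20 × 0.509 = 3.05 mm, which is 3.05/70.2 = 4.4% of baseline.
- Variance among those selected: 400 × (1 + aλ − λ²) = 194.5. Variance of the change: 0.3² × 194.5 + 400 × (1 − 0.7²) = 221.5, so its SD is 14.9 mm.

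Simulated trials with no treatment effect in this case:

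| Quantity | Entry reading as baseline | Visit 2 reading as baseline (all correlations 0.7) |
|---|---|---|
| Paired t-test rejects, n=15 | about 11% | 5% |
| Paired t-test rejects, n=20 | about 14% | 5% |
| Subject falls 15% or more | about 30% | about 24% |
| Group mean falls 15% or more, n=15 | about 2% | under 1% |
| Group mean falls 15% or more, n=20 | about 1% | under 1% |

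The 24% is random variation that any single baseline leaves. Selection adds 30 − 24 = about 6 subjects per 100.

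**Sensitivity.** Over μ 40 to 70 (steps of 5), σ 15, 20 and 25, and r 0.5 to 0.9 (steps of 0.1), which is 105 combinations, the fall runs from 0.3 to 13.4 mm (0.4% to 20%), median 3.4 mm (4.8%). It is below 2% in 20 combinations. It reaches 15% in 5, all with a mean of 45 or less and r of 0.6 or less. With r of 0.7 or more the range is 0.3 to 8.0 mm (up to 12%). With μ of 60 or more as well, the maximum is 4.2 mm (5.7%).

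**If correlation decays with time.** Take μ = 60, σ = 20, correlation 0.8 from Visit 1 to Visit 2 and 0.6 from Visit 1 to 6 months. The total fall is 0.4 × 20 × 0.509 = 4.1 mm, of which 0.2 × 20 × 0.509 = 2.0 mm occurs before Visit 2. A Visit 2 baseline removes that half. Rejection with no effect goes from about 14% to 7–8% (n=15) and from about 17% to 8–9% (n=20), for a correlation of 0.6 to 0.7 between Visit 2 and 6 months.

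**The case against.** The strongest objection is to the premise. The heading "6.7 Study Procedure Flow Chart" shows that a schedule of assessments exists, but its content is absent from this copy, and that is not a gap in the plan. The visit text is not a full schedule either: section 9.1 lists "Blood draw for lab tests" as a source of risk, yet no visit mentions one. No sentence names the Visit 1 VAS as baseline, and 4.3 does not say that its threshold applies to that reading. A reader might infer that the Visit 1 score must be both the entry test and the baseline. That is a likely reading of 6.1, but the documents do not establish it. This objection stands, and the point is conditional for that reason.

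Second, the size rests wholly on assumptions, and the largest values need a low screened mean and weak correlation. Pain refractory to 3 months of therapy, together with "Subjects will not initiate any new pain therapy or escalate current therapy for 1 month prior to GAE", may favour stable scores. This stands too. It limits the effect but does not remove it while the correlation is below 1.

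Third, an open-label, single-arm pilot is a legitimate, openly stated design, and other sources of bias remain whatever baseline is used. That is true, and no control arm is asked for here. It is a reason for modest severity and plainer wording in 8.2; it does not justify leaving the baseline undefined.

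**Conclusion.** The point holds conditionally. If the entry VAS is also the baseline, some regression to the mean is expected in the VAS change. The direction follows from the selection; the size cannot be derived from the documents. In the assumed case (mean 60 mm, SD 20 mm, correlation 0.7) the t-test's false-positive rate roughly doubles or more, from 5% to 11–14%, while the untreated fall is well short of the 15% criterion. The bias is negligible if patients lie well above 50 mm and reliability is high.

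Two stronger readings are not supported. One is that selection alone would produce a 15% mean improvement: in the assumed case this happens in about 1–2% of trials. The other is that the main efficacy result is compromised: the sample size rests on WOMAC, which has no entry threshold and is affected only through its correlation with the VAS. This is a cheap improvement of lower severity.

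**What to change.** - Take the VAS at Visit 2, after consent and before sedation and GAE. Take the WOMAC then too; otherwise the two efficacy baselines could be up to 4 weeks apart. If the flow chart already lists Visit 2 readings, designate those.
- Name these readings in 7.2 and 8.2 as the baseline for change and for the percentage criteria.
- Keep the Visit 1 VAS for eligibility, and report the Visit 1 to Visit 2 change descriptively.
- In 8.2, replace the wording that attributes the change to the procedure with *changes after GAE*. Placebo response, natural course and unblinded self-report remain after this fix.

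Cost: a few minutes at a visit already scheduled. Downsides: pre-procedure anxiety may affect the reading, and the bias is only partly removed if correlation decays over time.

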6.2 Visit 2 GAE

GAE will be performed as described in part 5.1 above within 4 weeks of Visit 1. Subjects will be given a pager number to reach a physician 24 hours a day to report any adverse symptoms and receive medical advice.

6.3 Visit 3 -1 Day Follow-up

Subjects will be seen in clinic or contacted by phone or by teleconference per the subject's preference the day following GAE (+3 days). As most complications of the procedure will be evident within this time period, this visit is to evaluate for early AE's. If AE is suspected based on change in pain scores or functionality, an MRI will be obtained for further evaluation.

6.4 Visit 4 - 1 Month Follow-Up

Subjects will be seen in clinic 30 +/- 7 days following GAE. The WOMAC questionnaire and VAS pain score will be completed and subjects will be evaluated for possible adverse events. An MRI of the treated knee will be acquired.* Subjects will also provide an update about the necessity/frequency of pre-established conservative therapies.

**MRI is only scheduled at one month in order to evaluate for non-target ischemic injury. These types of injuries will become apparent as early as 24 hours after embolization. Infarcted tissue will still be detectable at one month. Based on our experience with embolization in other areas, it is thought extremely unlikely that new ischemic injury related to the procedure will develop after the one-month follow-up. Additionally, findings that would be detected on later scans may be unrelated to the procedure and confound the data.*

6.5 Visit 5 - 3 Month Follow-Up

Subjects will be seen in clinic or contacted by phone or by teleconference per the subject's preference 90 +/- 10 days following GAE. The WOMAC questionnaire and VAS pain score will be completed and subjects will be evaluated for possible adverse events. Subjects will also provide an update about the necessity/frequency of pre-established conservative therapies. If AE is suspected based on change in pain scores or functionality, an MRI will be obtained for further evaluation.

6.6 Visit 6 - 6 Month Follow-Up

Subjects will be seen in clinic or contacted by phone or by teleconference per the subject's preference 180 +/- 10 days following GAE. The WOMAC questionnaire and VAS pain score will be completed and subjects will be evaluated for possible adverse events. Subjects will also provide an update about the necessity/frequency of

pre-established conservative therapies. If an AE is suspected based on change in pain scores or functionality, an appropriate work-up will be performed which may include MRI.

6.7 Study Procedure Flow Chart

7.0 Safety and Effectiveness Assessments

7.1 Safety Assessments

Subjects will be observed for several hours after GAE to monitor for immediate complications to include bleeding, infection and acute ischemia of the lower extremity. The subjects will be given a phone number that they can call to reach the principal investigator or designee if they believe they have developed a complication of the procedure.

7.2 Effectiveness Assessments

Technical success will be defined as devascularization of hypervascular synovium at the affected knee. This will be determined during the procedure. Clinical success will be defined as a 16% reduction of the baseline global WOMAC score at 6 month follow-up (primary outcome) and a 15% reduction of the baseline pain VAS score at 6 month follow-up (secondary outcome).

8.0 Statistical Plan

8.1 Sample Size Determination

Only one small study has examined the use of transcatheter arterial embolization for the treatment of knee pain secondary to OA (12). In that study, the baseline WOMAC total score (mean±SD) was 48.5±9.4. The primary outcome of this study is a 16% reduction in the baseline WOMAC total score. Using the baseline total score from that study, a sample size of 15 will have 80% power to detect a 16% difference (7.8 points) in means, assuming a standard deviation of 10 points. Conservatively, to protect against a potential lost-to-follow-up of 30%, 20 total subjects will be enrolled. This sample size also will ensure adequate power for the secondary outcome, a reduction in the VAS by 15% at 6 months follow-up.

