8.2 Statistical Methods

This is a pre-post analytical design and the primary statistical method will be a paired t-test, examining changes from baseline to 6 months. We will use a paired t-test to statistically measure changes resulting from the GAE procedure. Frequencies, including pre-post change, will be reported as percents with 95% confidence intervals. Continuous data will be reported as means with 95% confidence intervals. $P \leq 0.05$ will be considered to indicate statistical significance. All analyses will be performed using SAS software and confidence intervals will be reported as appropriate, including estimates for the appropriate sample size for a larger future study (v9.2, SAS Institute Inc., Cary, NC).

Any deviations from the previously described statistical plan will be described and justified in a protocol amendment and/or in the final report submitted to the IDE application. The causes of all missing values will be documented with the study data.

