8.3 Subject Population(s) for Analysis

A patient will be considered an evaluable study subject evaluable for data analysis per the following criteria, a written informed consent was obtained, he/she meets the inclusion and exclusion criteria, and received the GAE study procedure. All subjects with 6 month follow-up data will be included for analysis even if some follow up data is incomplete. Every attempt will be made to ensure that there is as little missing data

as possible including reminder phone calls and follow-up phone calls if a subject misses a visit.

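### Section 8.1 says enrolling 20 protects against 30% loss to follow-up, but 30% loss leaves 14 subjects, not the 15 needed for 80% power; the protection reaches only 25%.

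*Combined protocol and SAP*

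**What the plan says.** Section 8.1 takes a baseline WOMAC total of 48.5 (SD 9.4) from one earlier small study and says that "a sample size of 15 will have 80% power to detect a 16% difference (7.8 points) in means, assuming a standard deviation of 10 points". It then sets enrolment: "Conservatively, to protect against a potential lost-to-follow-up of 30%, 20 total subjects will be enrolled". It adds, for the pain VAS, "This sample size also will ensure adequate power for the secondary outcome", with no VAS mean, standard deviation or power.

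Three other sections decide what happens to a subject who is lost:

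- Section 8.2: "the primary statistical method will be a paired t-test, examining changes from baseline to 6 months", with significance at P ≤ 0.05.
- Section 8.3: "All subjects with 6 month follow-up data will be included for analysis even if some follow up data is incomplete".
- Section 4.6.2: "Subjects will only be replaced if they withdrew prior to undergoing GAE". The sentence before it keeps the recorded data of withdrawn subjects in the analysis.

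Section 4.2 separately expects all 20 subjects to complete.

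**The concern.** The enrolment sentence follows directly on the 15-subject requirement, so its natural meaning is that 15 evaluable subjects, and hence 80% power, survive a 30% loss. They do not. A reader who relies on Section 8.1 would credit the design with more tolerance for attrition than its own figures give, and the sentence presents the choice as a conservative one.

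Two gaps in the same paragraph make the calculation hard to check. The standard deviation of 10 is not labelled: a paired t-test depends on the standard deviation of the within-subject change, whereas the only one cited is a baseline value. The VAS statement has no inputs at all. Both matter somewhat more than usual here, because Section 2.0 makes sample size data for a future study a secondary aim.

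**Working it through.** **Inputs.** From Section 8.1: 15 evaluable subjects, 80% power, baseline mean 48.5, 16% reduction, SD 10, 30% loss, 20 enrolled. From Section 8.2: paired t-test, 0.05 level. Assumed: a two-sided test, and 10 as the SD of the change. Neither is stated.

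**Reproducing the plan's figure.** The effect is 0.16 × 48.5 = 7.76, which the plan rounds to 7.8. The standardised effect is d = 7.8/10 = 0.78. Exact power comes from the noncentral t distribution with n − 1 degrees of freedom and noncentrality d√n. For n = 15 the noncentrality is 0.78 × √15 = 3.02 and power is 80.2%, so the stated figure reproduces. The alternatives do not fit: a one-sided 0.05 test gives 89.0% at n = 15, and a normal approximation gives 85.6% and would need only 13 subjects.

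**The attrition step.** This needs no assumption about sidedness or SD.

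- Remaining after 30% loss: 20 × 0.70 = 14.
- Enrolment that keeps 15 after 30% loss: 15/0.70 = 21.4, so 22 (22 × 0.70 = 15.4).
- Largest loss at which 20 keeps 15: 1 − 15/20 = 25%.
- The figure 20 agrees with 15 × 1.30 = 19.5 rounded up, that is, adding 30% where dividing by 0.70 was needed. The plan does not state its formula, so this is only a likely explanation.

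**Power at each number analysed** (two-sided 0.05, SD of change 10):

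| Evaluable n | Loss from 20 | Power, 7.8 points | Power, 7.76 points | Largest SD of change for 80% power, 7.8 points |
|---|---|---|---|---|
| 14 | 30% | 77.0% | 76.6% | 9.6 |
| 15 | 25% | 80.2% | 79.8% | 10.0 |
| 20 | none | 91.1% | 90.8% | 11.8 |

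The last column is 7.8 divided by the standardised effect that gives 80% power: 0.8101, 0.7780 and 0.6604 for n = 14, 15 and 20.

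**Does anything else restore the fifteenth subject?** No. Replacement covers only withdrawals before the procedure. Keeping a withdrawn subject's recorded data does not supply the 6-month score that the paired test needs, and no imputation is described.

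**What the SD of 10 could mean.** If it is the SD of scores at a single visit, taken as equal at both visits, the SD of the change is 10 × √(2(1 − ρ)), where ρ is the correlation between baseline and 6 months:

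| ρ | SD of change | Power at n = 15 |
|---|---|---|
| 0 | 14.14 | 51.2% |
| 0.25 | 12.25 | 63.1% |
| 0.5 | 10.0 | 80.2% |
| 0.75 | 7.07 | 97.7% |

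The stated power therefore needs an SD of change of 10, either assumed directly or reached through a per-visit SD of 10 with ρ = 0.5. The plan gives no correlation.

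**VAS.** Section 4.3 requires a VAS above 50 mm, but the documents give no mean. For an assumed mean baseline, the largest SD of change that leaves 80% power for a 15% reduction is 0.15 × baseline divided by the same standardised effects:

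| Assumed mean baseline | n = 14 | n = 15 | n = 20 |
|---|---|---|---|
| 60 mm | 11.1 mm | 11.6 mm | 13.6 mm |
| 70 mm | 13.0 mm | 13.5 mm | 15.9 mm |
| 80 mm | 14.8 mm | 15.4 mm | 18.2 mm |

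Whether the true SD lies below these limits cannot be judged from the documents.

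**The case against.** The strongest reply is that this hardly matters. The shortfall is one subject and about 3 points of power, and it arises only if attrition reaches the full 30%, which the plan treats as a cautious upper figure. Full completion is expected. The 3- and 6-month visits may be done by phone or teleconference (Sections 6.5 and 6.6), and Section 8.3 promises reminder and follow-up calls. At any loss up to 25% the plan meets its own target. All of this stands, and it is why the point is minor. It does not make the 30% statement correct.

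Read strictly, Section 8.1 also never says in so many words that 15 subjects or 80% power remain after 30% loss. That is true, but the sentence has no other evident purpose than to preserve the requirement stated just before it.

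On the SD, the authors' 10 may be a rounded-up score SD and not an SD of change. That is possible, so they should confirm which they meant. Labelling it as the SD of the change is numerically right either way, because that is the value the stated power requires.

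On the VAS, the SD limits rest on baselines assumed here and show only what the claim would need. Stating the plan's own assumptions, or deleting the sentence, is enough.

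**Conclusion.** The concern holds, as a minor error in the text. Enrolling 20 protects the 15-subject requirement against 25% loss, not 30%. At 30% loss 14 subjects remain and power is about 77%, against the 80% target; with no loss it is about 91%. The counts and the 25% limit follow from the plan's figures alone. The power values also assume a two-sided test and an SD of change of 10, the combination that reproduces the plan's own 80% at 15 subjects. The unlabelled SD and the bare VAS statement are secondary gaps in reporting. Neither shows that the study is underpowered.

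**What to change.** Revise Section 8.1 as follows.

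1. Replace the attrition sentence with wording such as: *Twenty subjects will be enrolled. This keeps 15 evaluable subjects (80% power) at up to 25% loss; at 30% loss 14 remain, with about 77% power; with no loss, power is about 91%.*
2. Label the 10 points as the standard deviation of the within-subject change, and state that the test is two-sided. If a per-visit SD was meant, also state the correlation of 0.5 that the calculation then implies.
3. For the VAS, give the assumed mean baseline and the SD of change at which 80% power holds (for example, at an assumed 70 mm, at most about 13.0 mm for 14 subjects, 13.5 mm for 15 or 15.9 mm for 20), or delete the sentence.

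The cost is wording only: no extra subjects and no change to the analysis. The stated power at 30% loss becomes slightly less favourable, 77% instead of 80%. Enrolling 22 would also make the 30% claim true, at the cost of two more subjects, but a pilot of this kind does not need it.
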